7 STUDY ASSESSMENTS AND PROCEDURES

Study procedures and their timing are summarized in the Schedule of Assessments.

Immediate safety concerns should be discussed with the sponsor immediately upon occurrence or awareness to determine if the participant should continue or discontinue study intervention.

Adherence to the study design requirements, including those specified in the SoA is essential and required for study conduct.

All screening evaluations must be completed and reviewed to confirm that potential participants meet all eligibility criteria. The investigator will maintain a screening log to record details of all participants screened and to confirm eligibility or record reasons for screening failure, as applicable.

Procedures conducted as part of the participant's routine clinical management (e.g., blood count) and obtained before signing of the informed consent form (ICF) may be utilized for screening or baseline purposes, provided the procedures met the protocol-specified criteria and were performed within the time frame defined in the SoA.

7.1 Efficacy Assessments

Tumor Assessment (RECIST)

Staging imaging will be performed by CT scan according to the SoA. Tumor Response will be evaluated at each time point. Radiographic response will be measured according to RECIST 1.1 (Eisenhauer 2009). All imaging will be interpreted locally by the investigational site radiologist. The same method of imaging used at baseline must be used at each follow up evaluation for treatment response.

The number of subjects exhibiting PR, CR and PR+CR will be reported at Months 6, 12, 18 and 24.

RECIST 1.1 Tumor Response Evaluation Definitions of the criteria used to determine objective tumor response for target lesions (Eisenhauer, 2009)	
Complete Response (CR):	Disappearance of all target lesions. Any pathological lymph nodes (whether target or non-target) must have reduction in short axis to <10 mm.
Partial Response (PR):	At least a 30% decrease in the sum of diameters of target lesions, taking as reference the baseline sum diameters.
Progressive Disease (PD):	At least a 20% increase in the sum of diameters of target lesions, taking as reference the smallest sum on study (this includes the baseline sum if that is the smallest on study). In addition to the relative increase of 20%, the sum must also demonstrate an absolute increase of at least 5 mm. (Note: the appearance of one or more new lesions is also considered progression)
Stable Disease (SD):	Neither sufficient shrinkage to qualify for PR nor sufficient increase to qualify for PD, taking as reference the smallest sum diameters while on study.

Definitions for Response Evaluation

Progression-Free Survival

Progression-free survival (PFS) is defined as the time from the date of registration (Phase 1) or randomization (Phase 2), to first occurrence of local and/or regional NSCLC progression, distant metastases from NSCLC, second primary tumor, or death due to any cause, whichever occurs first. Patients without progression and who did not die are censored at their last evaluable tumor response assessment.

Local and Regional Control

Local and regional control is defined as the time from registration (Phase 1) or randomization (Phase 2), to any local and regional recurrence or progression of NSCLC. Local enlargement, marginal failures, involved lobe failure, or local relapse will be considered failure events for local control. Regional failure with nodal progression (new lesions) in the mediastinum will be a failure event for regional control. Distant metastases from the index lung cancer or a second primary tumor are not considered local progression. Patients who die with lung cancer, but who do not have documented local progression will be considered non-failures for local progression and will be censored on the day of their death. Patients who die without progressive lung disease and have no documented local progression will be considered non-failures for local progression and will be censored on the day of death.

Overall Survival

Overall survival (OS) is defined as the time from registration (Phase 1) or randomization (Phase 2), to death due to any cause. Survival status should be assessed every 6 months following progression through 24 months. All subjects who are in the Survival Follow-up Phase and not known to have died prior to sponsor requests for additional survival status timepoints may be contacted at that time to confirm survival status. Patients who have not died are censored at the date last known to be alive.

Distant Metastasis Rate

Distant metastasis rate refers to cancer that has spread from the original (primary) tumor to distant organs or distant lymph nodes (outside mediastinum).

7.1 Safety Assessments

Planned time points for all safety assessments are provided in the Schedule of Assessments (Table 1).

Physical Examinations

A complete physical examination will include, at a minimum, assessments of the Cardiovascular, Respiratory, Gastrointestinal and Neurological systems. Temperature and weight will also be measured and recorded. Height should only be recorded at Screening (Visit 1). The physical examination should be performed by a physician or health professional listed on the Form FDA 1572 and licensed to perform physical examinations.

Vital Signs

Vital sign measurements prior to each infusion will include pulse rate, respiratory rate, systolic and diastolic blood pressure. Pulse and blood pressure readings will be taken after the subject has been at rest for 2 minutes before each infusion and after infusion prior to SBRT. Respiratory rate does not need to be repeated.

Electrocardiograms

A 12-lead ECG recording will be conducted using an ECG machine that automatically calculates the heart rate and measures PR, QRS, QT, and QTcF intervals. The recordings should be as close as possible to corresponding PK sampling (+/- 10 minutes from the PK draw) per the SOA. The pre- and post-dose ECG should be done in triplicate.

Pneumonitis Assessment

The following will be completed for the pneumonitis assessment:

- NCI-CTCAE scale (https://ctep.cancer.gov/protocoldevelopment/electronic_applications/docs/CTCAE_v5_Quick_Reference_8.5x11.pdf)
- CT of chest with IV contrast, unless contrast is medically contraindicated; evaluate for presence of the descriptive items listed in Appendix 4
- Spirometry including pulse oximetry [SpO₂], forced vital capacity [FVC], first expiratory volume in the first second [FEV1], and diffusing capacity of the lungs for carbon monoxide (DLCO).
- Medications will be recorded, including inhalers and steroids
- Hemoglobin (Hb) monitoring (interference if Hb lower than 7 grams per deciliter needs repetition of spirometry assessment after Hb correction, e.g., transfusion)
- Any additional testing should be recorded in the CRF as unscheduled

Lung function

Clinically, radiation induced pulmonary injury can manifest within weeks to months following radiotherapy. However, most cases are reported within the first 8 months. The classic triad of symptoms includes dyspnea on exertion, non-productive cough, and hypoxemia, though low-grade fevers are also common. Physical exam findings can include pleural friction rub, moist rales as well as signs of consolidation. These manifestations may be complicated by the presence of pre-existing lung disease such as COPD or emphysema. The incidence of symptomatic pneumonitis has dropped with introduction of motion management and other modern RT techniques (Jain 2018). The most used grading system is the Common Terminology Criteria for Adverse Events (CTCAE) published by the National Cancer Institute:

https://ctep.cancer.gov/protocoldevelopment/electronic_applications/docs/ctcae_v5_quick_reference_5x7.pdf

Objectively, the effect of pneumonitis on lung function can be assessed using pulmonary function tests (PFTs), a clinical gold standard. Borst, et al. (2005) reported a decrease in first expiratory volume in 1 s (FEV1) as early as three months post RT; however, most were observed at 6 months. Diffusion capacity of lungs (DLCO) is described as the most prominent PFT

parameter predictive of and impacted by radiation pneumonitis (Stone 2015, Jain 2018). Our primary efficacy measurement of lung function will be prevention of significant falls in DLCO by standard pulmonary function testing. DLCO can be affected by different factors, including alveolar volume and hematologic assessment, as well as smoking, pre-existent chronic obstructive lung disease (COPD), age and medication, including inhalers, oxygen supply and steroids.

In the follow-up portion of this trial, in addition to lung function, hemoglobin will be measured, and medication given for respiratory disease and radiation toxicities (See section 7.4), new anti-cancer treatments will be recorded through 24 months post SBRT completion, as well as smoking and COPD will be monitored throughout 12 months.

PFTs are not part of standard clinical routine follow-up of radiation therapy but can add significant information to radiological and clinical scoring of radiation induced lung injuries. In our study, we measure PFTs every six months in parallel to the radiological assessments (Videtic 2013, Takeda 2013, Ferrero 2015, Vansteenkiste 2014).

Declines in DLCO from baseline will be scored using the Radiation Therapy Oncology Group (RTOG) scale, in which:

- Grade 0 is <10% decline from baseline;
- Grade 1 is 10-25% decline from baseline;
- Grade 2 is >25%-50% decline from baseline;
- Grade 3 is >50%-75% decline from baseline;
- Grade 4 is >75% decline from baseline;
- Grade 5 is death.

7.2 Adverse Events and Serious Adverse Events

The definitions of an AE or SAE can be found in

Appendix 3. The Investigator is responsible for the detection and documentation of events meeting the criteria and definition of an AE or SAE as provided in this protocol. Throughout the study, AEs will be recorded in the source documents and on the appropriate pages of the CRF regardless of whether the AEs are considered related to GC4711/Placebo or SBRT. To avoid confusion, the AE should be recorded in standard medical terminology.

Adverse event(s) will be reported by the participant (or, when appropriate, by a caregiver, surrogate, or the participant's legally authorized representative).

The investigator and any qualified designees are responsible for detecting, documenting, and recording events that meet the definition of an AE or SAE and remain responsible for following up AEs that are serious, considered related to the study intervention or study procedures, or that caused the participant to discontinue the study intervention/study (see Section 5.4).

Time Period and Frequency for Collecting Adverse Events and Serious Adverse Events Information

All adverse events will be collected from the Day 1 dosing through 90 days post-SBRT completion to ensure collection of acute toxicities and up to 12 months for late radiation toxicities. Please see Section 7.4 for the definition of late radiation toxicities.

All SAEs will be recorded and reported to the sponsor or designee immediately and under no circumstance should this exceed 24 hours, as indicated in

Appendix 3. The investigator will submit any updated SAE data to the sponsor within 24 hours of it being available. Specific SAE reporting instructions are provided in a separate manual.

Method of Detecting Adverse Events and Serious Adverse Events

The method of recording, evaluating, and assessing causality of AEs and SAEs and the procedures for completing and transmitting SAE reports are provided in

Appendix 3.

Care will be taken not to introduce bias when detecting AEs and/or SAEs. Open-ended and non-leading verbal questioning of the participant is the preferred method to inquire about AE occurrences.

Follow-up of Adverse Events and Serious Adverse Events

After the initial AE/SAE report, the investigator is required to proactively follow each participant at subsequent visits/contacts. All SAEs will be followed until resolution, stabilization, the event is otherwise explained, or the participant is discontinued from the study. Further information on follow-up procedures is given in

Appendix 3.

Regulatory Reporting Requirements for Serious Adverse Events

Prompt notification by the investigator to the sponsor of an SAE is essential so that legal obligations and ethical responsibilities towards the safety of participants and the safety of a study intervention under clinical investigation are met.

The sponsor has a legal responsibility to notify both the local regulatory authority and other regulatory agencies about the safety of a study intervention under clinical investigation. The sponsor will comply with country-specific regulatory requirements relating to safety reporting to the regulatory authority, Institutional Review Boards (IRB)/Independent Ethics Committees (IEC), and investigators.

Investigator safety reports must be prepared for suspected unexpected serious adverse reactions (SUSAR) according to local regulatory requirements and sponsor policy and forwarded to investigators as necessary.

Treatment of Overdose, Misuse, Abuse

Study drug overdose is any accidental or intentional use of study drug in an amount higher than the dose indicated per protocol for a given subject.

Any study drug overdose during the study should be noted on the study medication eCRF.

All AEs associated with an overdose should both be entered on the Adverse Event eCRF and reported using the procedures detailed in Section 7.2. Reporting of Serious Adverse Events. If the AE associated with an overdose does not meet seriousness criteria, it must still be reported using the Galera Therapeutics Clinical Trial Report Form for SAEs and in an expedited manner but should be noted as non-serious on the form and the Adverse Event eCRF.

There is currently no specific treatment in the event of an overdose of GC4711. The investigator will use clinical judgment and standard supportive care to treat any overdose.

Adverse events associated with misuse or abuse will be appropriately reported as AEs or SAEs and monitored per Section 7.2.

An investigator who receives an investigator safety report describing an SAE or other specific safety information (e.g., summary or listing of SAEs) from the sponsor will review and then file it along with the Investigator's Brochure and will notify the IRB/IEC, if appropriate according to local requirements.

7.3 Pregnancy

The risks of treatment with GC4711 during pregnancy have not been evaluated. Male subjects and female subjects of childbearing potential who engage in sexual intercourse should use a barrier method of contraception throughout the study and for 30 days (females) or 90 days

(males) following the last dose of GC4711/Placebo. If a pregnancy is reported, the investigator should inform the sponsor within 24 hours of learning of the pregnancy and should follow the procedures outlined in Appendix 6.

7.4 Late Radiotherapy Toxicities

Late radiotherapy toxicities will be collected as per the Schedule of Assessments. Related, late radiation toxicities (Kang 2015) will be collected up to 12 months post SBRT and defined using NCI Common Terminology Criteria for Adverse Events (version 5.0).:

- Grade 1-5 Respiratory, thoracic and mediastinal disorders, including rib fractures
- Grade 1-5 esophagus, and
- Grade 3-5 cardiac events
- Grade 3-5 spinal cord/brachial plexopathy and vascular events

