Modern RT techniques have enabled more precise delivery of high ablative doses with improved sparing of surrounding normal tissue. For early-stage NSCLC, SBRT has become an alternative to surgery (Timmerman 2010). After initial demonstration of safety with SBRT for small peripheral NSCLC lesions, SBRT has been delivered to larger and more central lesions (Bezjak 2019), which identified SBRT dosing of 11.5 or 12 Gy x 5 fractions as associated with acceptable toxicity and with approximate 2-year rates for local control, overall survival, and progression-free survival of approximately 90%, 70%, and 55%, respectively. The practice is shifting toward 5 fractions specially for central localizations; however, a 3-fraction regimen is still accepted. Use of SBRT for larger or centrally located NSCLC is reported to increase the risk of toxicity with a larger volume of normal tissue exposure (Fakirs 2009, Woody 2015, Peterson 2016, Beak 2019). SBRT can induce inflammatory reactions and sequentially generate fibrosis and lung functional restrictions (Lu 2018). Individual risk of radiation-induced pneumonitis depends on the volume of lung treated and the radiation dose administered, as well as patient age and other treatment modalities used (immunotherapy itself has around 10% pneumonitis risk on its own (Zhao 2016, Mohamad 2018)). Central tumors have a higher complication risk because of the close relation to the major airways, esophagus, and major vessels. These tumors are treated with 5 or more fractions of SBRT (Lo 2009) to give normal tissue within the field more time to repair (Timmerman 2006). Radiation induced injury is a slowly developing process, developing radiological changes and symptoms around 3-6 months (mean 135 days) after treatment (Vide tic 2013, Takeda 2013, Jain 2018, Ferrero 2015). Approximately a quarter of patients encounter lung function decline, after a 5-fraction regimen SBRT (Stone 2015). A small portion of patients (approximately 10%) remain with a significant

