Inclusion and exclusion criteria ^e	X									
Registration/Randomization (Phase 1/Phase 2) ^e	X									
Medical history (includes smoking history)	X									
Demography	X									
Complete PE including height and weight	X								X	
ECOG Performance Status	X								X	
Vital signs ^f	X	X	X	X	X	X				
PK Blood samples ^g		X	X							
12-lead ECG ^h	X	X		X						
AE/SAE review ⁱ		X	X	X	X	X	X	X	X	
Concomitant medications/treatments and smoking review ^j	X	X	X	X	X	X		X	X	X
Survival Status								X	X	X
Serum pregnancy test (WOCBP only)	X									
Serum chemistry panel	X						X			
Complete blood count	X						X		X	
PT/INR, aPTT	X									
PFTs – SpO ₂ , FEV1, FVC and DLCO ^{k, n}	X								X	
CT chest for pneumonitis scoring ^k	X								X	X
CT (chest, abdomen, pelvis) ^k	X								X	X
GC4711/Placebo IV infusion ^l		X	X	X	X ^l	X ^l				
SBRT administration ^m		X	X	X	X ^m	X ^m				

AE = adverse event, BP = blood pressure, CBC = complete blood count, CT = computed tomography, CTCAE = Common Terminology Criteria for Adverse Events, DLCO = diffusion capacity of lung for carbon monoxide, ECG = electrocardiogram, ECOG PS = eastern cooperative oncology group performance status, FEV1 = forced expiratory volume in 1 second, FU = Follow-up, , IV = intravenous, PE = physical examination, PET = positron emission tomography, PFTs = pulmonary function tests, PK = pharmacokinetics, SAE = serious adverse event.

- a Screening evaluations should occur within 21 days of Treatment Day 1, except where otherwise noted
- b The Day 12 visit should occur 7 days after the last dose of SBRT \pm 5 days
- c The 30- and 90- day post SBRT completion visits should occur on or within 7 days after target date and may be performed remotely via telemedicine visits. The Months 6 and 12 post SBRT completion visits should occur \pm 7 days of target date.
- d The Month 18 and 24 post SBRT visits should occur \pm 14 days of target date.
- e Registration/Randomization should occur after all screening assessments are performed, eligibility is confirmed, and within 7 days of the first dose of SBRT. Confirmation of eligibility should include confirmation of diagnosis, histology and exclusion of distant disease by standard practice.
- f BP and HR should be taken prior to each infusion, monitoring possible hypotensive symptoms, please repeat before going from infusion to radiation site.

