- g PK blood samples should be drawn pre-and post- - infusion on Day 1 and Day 3. The end of infusion PK draw should be drawn within 10 minutes after the end of infusion and the ECG should be \pm 10 minutes from the PK draw.
- h The ECGs will be collected in triplicate pre- and post-infusion as close to PK draws as possible. The end of infusion PK draw should be drawn within 10 minutes after the end of infusion and the ECG should be \pm 10 minutes from the PK draw. A 12-lead ECG recording will be conducted using an ECG machine that automatically calculates the heart rate and measures PR, QRS, QT, and QTcF intervals.
- i AE/SAE collection will occur through 30 days post SBRT completion for treatment related adverse events, will continue through 90 days post SBRT completion for acute toxicities (all AEs/SAEs) and 1-year post SBRT completion for late radiation toxicities. Please see [Section 7.4](#) for the definition of late radiation toxicities. The DLT period is through 30 days post-SBRT for Phase 1 subjects. Please see [Section 7.5](#) for details on the DLT definition.
- j All medications taken from 30 days prior to dosing through 90 days post SBRT completion should be documented in source records and CRF. After 90 days post-SBRT, only medications used to treat late radiation toxicities should be recorded through 12 Months post SBRT completion, including inhalers, steroids, oxygen supply, etc. Additionally, any new anti-cancer therapy given in follow-up should be recorded in the CRF through 24 months post-SBRT or disease progression.
- k Imaging assessments performed as part of standard of care within 56 days of dosing will be accepted. Investigator Response Assessment should follow RECIST 1.1. Suspicion of progression should be confirmed with PET at 6 months. Radiographic assessment of pneumonitis will occur by evaluating for presence of descriptors listed in the table in Appendix 4.
- l GC4711 or placebo will be given prior to each dose of SBRT starting the first day of SBRT through the last day of SBRT. GC4711/placebo infusion should be completed within 180 minutes prior to the start of SBRT. For patients treated with a 3-fraction SBRT regimen, only 3 doses of GC4711 will be administered.

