4.2 Study Duration for Participants

The study duration for participants is expected to be approximately 25 months. This includes a 21-day screening period, a treatment period of approximately 5-10 days, and long-term follow-up for 24 months. All subjects are evaluated 30 days after SBRT and 6, 12, 18 and 24 months post-SBRT.

If a participant experiences progressive disease prior to 24 months post-SBRT completion, they will continue for survival follow-up until end of study (24 months following the last administration of SBRT). No additional tumor assessments will be required after progression; however, adverse events for long term radiation toxicities will continue through 12 months post SBRT completion and survival follow up will continue through 24 months post SBRT completion.

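### Section 7.4 makes relatedness a condition for collecting toxicity after Day 90, Section 7.2 says the opposite, and the protocol's own timing for lung injury falls in that window

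*Combined protocol and SAP*

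**What the plan says.** **Collection windows.** Section 7.2 states: "All adverse events will be collected from the Day 1 dosing through 90 days post-SBRT completion". It then continues to 12 months for late radiation toxicities and refers to Section 7.4 for their definition. Table 1 footnote i gives the same window ("1-year post SBRT completion for late radiation toxicities") with the same reference, and so does the synopsis under safety monitoring. Section 4.2 adds that, after progression, "adverse events for long term radiation toxicities will continue through 12 months post SBRT completion".

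**The condition.** Section 7.4 opens its definition with "Related, late radiation toxicities". It lists respiratory, thoracic and mediastinal disorders (including rib fractures) and esophageal events at Grade 1-5, and cardiac, spinal cord or plexus and vascular events at Grade 3-5. No other section attaches relatedness to late toxicity as a limit on collection.

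**The counter-text.** The opening of Section 7.2 says that throughout the study events go into source and CRF "regardless of whether the AEs are considered related to GC4711/Placebo or SBRT". Appendix 3 requires the investigator to assess relatedness to GC4711 and to SBRT for each event.

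**Timing of lung injury.** The synopsis rationale has it "developing radiological changes and symptoms around 3-6 months (mean 135 days) after treatment". Section 2.1 gives 4-6 months with the same mean. Section 7.1 (Safety Assessments, lung function) says most cases are reported within 8 months.

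**The concern.** Reduced lung toxicity is one of the two benefits proposed for GC4711, and the Phase 2 secondary objectives compare acute and late toxicity between arms. If Section 7.4 is followed as written, the rule for recording a clinical event changes at Day 90, shortly before the time at which the protocol expects lung injury to appear.

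By the protocol's own account, attribution is difficult here. Section 7.1 says that COPD or emphysema may complicate the picture, and the synopsis says that lung function decline can be hard to distinguish from recurrence. Under Section 7.4, dyspnoea or cough put down to COPD, infection or tumour need not be reported as a late toxicity, and an event that is not reported cannot be re-adjudicated later. With up to 20 Phase 2 sites, the conflict between Sections 7.2 and 7.4 also lets sites apply different rules in good faith.

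**Working it through.** **1. The texts side by side.**

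| Place | After Day 90, to Month 12 | Relatedness required? |
|---|---|---|
| 7.2, opening | events recorded throughout the study | No, expressly |
| 7.2, time period | late radiation toxicities, defined in 7.4 | Not stated; refers to 7.4 |
| Table 1, footnote i | late radiation toxicities, defined in 7.4 | Not stated; refers to 7.4 |
| 4.2 | long-term radiation toxicities | Not stated |
| 7.4 | listed categories and grades | Yes |

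The references give Section 7.4 the stronger claim to govern, but the opening of Section 7.2 contradicts it directly.

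**2. Days.** 135 - 90 = 45 days after all-event collection ends. 365 - 135 = 230 days before late collection ends. Eight months is 8 x 30.44 = about 244 days, also inside 12 months.

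**3. Share of onsets after Day 90.** The mean of 135 days is from the protocol. No SD is given, so the SD and the shape are assumptions. Normal: share = 1 - Phi((90 - 135)/SD). Lognormal: s² = ln(1 + (SD/135)²), mu = ln(135) - s²/2, share = 1 - Phi((ln 90 - mu)/s). The same formulas with 365 in place of 90 give the share after Month 12.

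| SD (days) | Normal, >90 | Lognormal, >90 | Normal, >365 | Lognormal, >365 |
|---|---|---|---|---|
| 30 | 93.3% | 95.9% | 0.0% | 0.0% |
| 45 | 84.1% | 86.1% | 0.0% | 0.1% |
| 60 | 77.3% | 77.1% | 0.0% | 0.5% |
| 90 | 69.1% | 64.3% | 0.5% | 2.6% |
| 120 | 64.6% | 56.0% | 2.8% | 4.6% |

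For SD 75, the normal model gives 1 - Phi(-0.60) = 72.6%. A majority falls after Day 90 in every case tried.

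**4. Illustrative count.** Section 2.1 cites 9% to 28% for clinical pneumonitis needing medical intervention.
- Events in 66 patients: 66 x 0.09 = 5.9 and 66 x 0.28 = 18.5.
- After Day 90, normal model, SD 45-75: 5.9 x 0.726 = 4.3 to 18.5 x 0.841 = 15.5.
- If 20% of those are judged unrelated (assumed): 4.3 x 0.20 = 0.9 to 15.5 x 0.20 = 3.1, so about 1-3 events over both arms.
- Over the whole table (56.0% to 95.9%): 5.94 x 0.560 x 0.20 = 0.7 to 18.48 x 0.959 x 0.20 = 3.5.
- With the roughly 10% symptomatic rate at 6 months in Section 2.1: 6.6 x 0.726 x 0.20 = 1.0 to 6.6 x 0.841 x 0.20 = 1.1.

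**5. What the condition does not touch.** Appendix 4 descriptors on chest CT, DLCO and spirometry at Months 6 and 12, and respiratory medication to Month 12 (concomitant-medication section) need no relatedness call. Table 1 has no row for CTCAE pneumonitis scoring and no visit between Day 90 and Month 6. The AE/SAE review row is therefore the only scheduled route for symptomatic, graded events.

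**The case against.** **There may be no filter.** The opening of Section 7.2 can be read as governing the whole study, with Section 7.4 merely naming a class of event. This stands in part: the documents contain a contradiction, not a settled rule. But Section 7.2 itself sends the reader to Section 7.4 for what is collected after Day 90, so a site following that reference would apply the condition.

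**Lung injury is measured by other means.** Clinical and radiological pneumonitis scoring over 12 months is a Phase 2 endpoint, and the pneumonitis assessment in Section 7.1 lists the CTCAE scale, CT and spirometry with no relatedness condition. Treated breathlessness also leaves a trace in the medication record, although Table 1 footnote j is narrower than the medication section on this. A reader might infer that events judged unrelated would never be recorded at all; these sources show that this goes too far. They do not replace graded symptoms, however: the synopsis says radiological changes are not always accompanied by clinical symptoms.

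**The loss would not favour an arm.** A reader might infer differential loss, because tingling and hypotension were seen on GC4711 in healthy volunteers and the comparator is saline. The documents do not support that. Site staff other than pharmacists are blinded, those effects were transient infusion effects, and both arms receive the radiation to which late events would be attributed. The objection stands.

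**The size is soft.** Section 2.1 ties the 135-day mean to injury that is mostly radiological, while the 9% to 28% refers to pneumonitis needing intervention. Combining them is an approximation, and the SD and the 20% are assumed. This also stands.

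**Conclusion.** Sections 7.2 and 7.4 conflict on whether relatedness is a condition for recording toxicity after Day 90. If Section 7.4 is followed, symptomatic CTCAE-graded events judged unrelated could go unrecorded as toxicity at the time when the protocol expects lung injury to peak. The consequence is mainly non-differential under-ascertainment of the clinical component; the radiographic and functional components are unaffected. The size cannot be derived from the documents. About 1-3 events in 66 patients is an illustration resting on an assumed spread of onset and an assumed 20% judged unrelated. That is modest, but it matters with about 33 patients per arm and costs little to avoid.

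A reader might also infer that stopping event collection at Month 12 is an error, because the row for "CT chest for pneumonitis scoring" is marked at Months 18 and 24 while AE review is blank there. The documents do not support this. The 12-month limit is consistent across the sections and matches the late-toxicity endpoints in Section 3. Day 135 and the 8-month figure both fall inside it, and the models above put at most 4.6% of onsets beyond it. Extending collection to Month 24 would be a preference.

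**What to change.** Delete relatedness as a condition of collection in Section 7.4, and align Sections 7.2 and 7.4 and Table 1 footnote i on one rule: from Day 90 to Month 12, every event in the Section 7.4 categories and grades is recorded whatever its judged cause. Relatedness to GC4711 and to SBRT stays as the attribute that Appendix 3 already requires.

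In Section 8.5 or the SAP, specify a summary of all-cause respiratory toxicity by arm from Day 1 to Month 12, with related-only events as a sensitivity analysis. The respiratory category covers Grade 1-5 after Day 90, so it can be summarised as one period. The cardiac, spinal cord or plexus and vascular categories are limited to Grade 3-5 after Day 90, so a similar summary of those would need the same grade limit before Day 90.

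The cost is a protocol amendment and some extra entries at the existing Month 6 and Month 12 visits; no visit or procedure is added. The downside is that some unrelated COPD or infection events will enter the listing, which the relatedness attribute lets the analyst separate. If patients are already past Day 90 when the change takes effect, they should be identifiable, since their events may have been collected under the narrower rule.
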